4.3 Method of Assignment of Subjects to Treatment Groups

4.4 Blinding

A blinded design was not used in PX01 for flortaucipir exposure because all subjects received flortaucipir F 18. Subjects and investigators were blind to lanabecestat treatment throughout the trial.

4.5 Determination of Sample Size

This study will include up to 205 subjects who have a valid baseline flortaucipir scan, and a change from baseline value of CDR-SB at 18 months. In Study TZAX, which had a similar design and entry criteria, approximately 75% of subjects were rated as τ AD++ and 25% were rated as non- τ AD++. Among non- τ AD++ subjects (reference group), approximately 40% had an increase of 1 point or more on CDR-SB at 18 months follow up visit. Assuming a distribution of visual reads and CDR-SB change in this study is

Avid Radiopharmaceuticals
Study ¹⁸F-AV-1451-PX01

Statistical Analysis Plan

similar to that for TZAX, a sample of 205 subjects will provide 90% power to detect a risk ratio of 1.65 or larger, under a two-sided type I error rate of 5%.

5 CHANGES IN THE CONDUCT OF THE STUDY OR PLANNED ANALYSES

5.1 Changes in the Conduct of the Study

There were no changes in the conduct of the study at the time of preparing this SAP.

Avid Radiopharmaceuticals
Study ¹⁸F-AV-1451-PX01

Statistical Analysis Plan

6 BASELINE, EFFICACY AND SAFETY EVALUATIONS

6.1 Schedule of Evaluations

Study Procedure	Screening	Randomization/ Baseline									
Visit Number	V1	V2-V4	V6	V8	V10	V12	V14	V16	V20	V30	ED
Study Month (m)			3m	6m	9m	12m	15m	18m	24m	156w	
Tau Addendum											
Interval for Visit (d)					±7	±10		±7	±10	±7	
Flortaucipir PET Imaging		X			X	X		X	X	X	
Efficacy Measures											
CDR-SB	X			X		X		X	X		X
MMSE	X		X	X		X		X	X		X
ADAS			X	X		X	X	X	X		X
FAQ		X		X		X		X	X		X

Avid Radiopharmaceuticals
Study AV-1451-PX01

Statistical Analysis Plan

6.2 Time Point Algorithms

6.2.1 Windows

For all analyses, results will be summarized at the planned study visit they were obtained. Data was collected in weeks in the AZES study, therefore the following conversion will be used to analyze in months:

Weeks	Months
13	3
26	6
52	12
65	15
78	18
104	24

6.3 Screening and Baseline Assessments

Baseline cognitive and functional assessments will include ADAS-Cog11, MMSE, CDR-SB, and FAQ. Baseline will be defined in the same manner as in the AZES study.

6.4 Efficacy Variables

6.4.1 Primary Efficacy Variable(s)

6.4.1.1 Tau Status Based on Flortaucipir

Flortaucipir images were visually assessed by five independent readers blinded to all demographic and clinical data information of the subjects. The majority read (i.e., the tau status for which 3 or more readers have agreed upon) was used as the tau status.

For the visual reads, the images were classified as either τ AD++ (a pattern indicating spread of aggregated tau beyond the PLT lobe or occipital lobe), τ AD+ (a pattern indicating aggregated tau confined to PLT and/or occipital lobe) or τ AD- (inconsistent with an AD pattern). See table below for details.

Read Outcome		Objective Imaging Features
Not Consistent with AD pattern (τ AD-)		No increased neocortical activity, or increased neocortical activity isolated to mesial temporal, anterolateral temporal, and/or frontal regions.
AD pattern	τ AD +	In either hemisphere, increased neocortical activity in the posterolateral temporal (PLT) or occipital region(s).
	τ AD ++	In either hemisphere, increased neocortical activity in the parietal/precuneus region(s) or frontal region(s) with increased

Avid Radiopharmaceuticals
Study AV-1451-PX01

Statistical Analysis Plan

	uptake in the PLT, parietal, or occipital region(s).
--	--

For the purposes of these efficacy analyses, image reads will be contrasted in the following ways: τAD^{++} vs. non- τAD^{++} (τAD^{+} and τAD^{-}); τAD (τAD^{++} and τAD^{+}) vs. τAD^{-} ; τAD^{++} vs. τAD^{-} .

6.4.1.2 Clinical Dementia Rating (CDR) Scale (Berg, 1988)

The CDR examines 6 categories of cognitive functioning domains. Each domain is scored on a scale ranging from 0 to 3 (including 0.5). A CDR-SB will be generated as the sum of the values in each of the six domains. The CDR-SB sum scores ranges from 0-18, where higher scores indicate greater cognitive impairment. CDR was scheduled to be performed at screening, 6 months, 12 months, 18 months, and 24 months post-baseline. CDR-SB will be used as a continuous scale in exploratory objective analysis, when assessing the average CFB by tau status.

For the primary analysis, the CDR-SB score CFB will be dichotomized in two groups: CDR-SB score change 1 point or more at 18 months, or otherwise.

The CDR Global score (a global rating of dementia) was derived based on CDR item/domain values. CDR global will be dichotomized in two groups for exploratory analysis: any change in CDR global or otherwise.

Any CDR measurement collected outside of this intended visit schedule (e.g. Early Discontinuation) will not be included in the efficacy analysis.

6.4.2 Additional Efficacy Variables

6.4.2.1 Cognitive Assessments

These additional cognitive assessments from AZES will be analyzed:

Mini-Mental State Examination (MMSE)

The MMSE (Folstein et al., 1975) is a brief instrument used to assess cognitive function in elderly patients. The range for the total MMSE score is 0 to 30, the sum of each correct answer, with higher scores indicating better cognition. MMSE was scheduled to be collected at screening, 3 months, 6 months, 12 months, 18 months, and 24 months post-baseline. The score on a continuous scale will be used for secondary and exploratory analyses when assessing the average CFB by tau status. Any measurement collected outside of this intended visit schedule (e.g. Early Discontinuation) will not be included in the efficacy analysis.

Alzheimer's Disease Assessment Scale—Cognitive subscale

The ADAS (ADAS-Cog; Rosen et al. 1984) was designed to assess the severity of the dysfunction in the cognitive and non-cognitive behaviors characteristic of persons with AD. Although AZES reported ADAS-Cog13 as its primary endpoint, ADAS-Cog11 (a subset version of ADAS-Cog13 comprising of 11 questions) will be chosen for the PX01 analyses to remain consistent with other historical Avid studies. The cognitive subscale ADAS-Cog11, consists of 11 items assessing areas of function most typically impaired in AD: orientation, verbal memory, language, and praxis. The overall score for ADAS-Cog11 ranges from 0 to 70, with higher scores indicating greater disease severity, and is calculated as the sum of all 11 individual component scores. ADAS total score will be used as a continuous variable for the secondary and exploratory analyses to assess the average CFB by tau status. ADAS was scheduled to be collected at randomization (baseline), 3 months, 6 months, 12 months, 15 months, 18 months, and 24 months post-baseline. Any measurement collected outside of this intended visit schedule (e.g. Early Discontinuation) will not be included in the efficacy analysis.

Pfeffer Functional Activities Questionnaire (FAQ), (Pfeffer et al. 1982)

Functional status is conceptualized as the “ability to perform self-care, self-maintenance and physical activities.” The FAQ was developed to assess instrumental activities of daily living involving higher level functional skills such as shopping alone, writing checks, remembering appointments, etc. The FAQ asks the informant to rate the patient’s ability using the following scoring system: Dependent = 3; Requires assistance = 2; Has difficulty but does by self = 1; Normal = 0; Never did [the activity] but could do now = 0; Never did and would have difficulty now = 1. The sum scores ranges from 0-30, where higher scores indicate greater functional impairment. FAQ sum score will be used as a continuous variable in secondary objective analysis, when assessing the average CFB by tau status. FAQ was scheduled to be collected at randomization (baseline), 6 months, 12 months, 18 months, and 24 months post-baseline. Any measurement collected outside of this intended visit schedule (e.g. Early Discontinuation) will not be included in the efficacy analysis.

6.4.2.2 Clinically Meaningful Deterioration

The cognitive/functional assessments from 6.4.2.1 will be dichotomized to allow for the assessment of risk of clinically significant deterioration. Subjects will be categorized to these groups by the criteria accordingly.

CDR-SB: clinically significant deterioration is defined as a 1 point or more increase from baseline.

MMSE: clinically significant deterioration is defined as 3 points or more decrease from baseline.

Avid Radiopharmaceuticals
Study AV-1451-PX01

Statistical Analysis Plan

FAQ: clinically significant deterioration is defined as 3 points or more increase from baseline.

ADAS-Cog11: clinically significant deterioration is defined as 4 points or more increase from baseline.

CDR Global: CDR global CFB will also be categorized as any increase (change >0) versus no change or decrease (change <= 0).

7 STATISTICAL METHODS

7.1 Definitions and Conventions

All analysis will be performed using SAS version 9.2 or higher.

Data will be summarized using descriptive statistics (number of subjects [n], mean, standard deviation [SD], median, minimum [min], and maximum [max]) for continuous variables and frequency counts and percentages for discrete variables. Percentages will be rounded to one decimal place, except 100% will be displayed without any decimal places and percentages will not be displayed for zero counts.

The tables and listings will be numbered using a decimal system to reflect main levels of unique tables and listings and sub-levels of replicate tables and the listings with maximum two digits per level (e.g., Table XX.YY.ZZ...). Tables will be numbered as 14.YY.ZZ. Baseline analysis will be reported in table series 14.1, and efficacy analysis in series 14.2. Listings will be numbered as 16.YY.ZZ.

Unless otherwise specified, hypothesis testing will be two-sided with type I error rate of 0.05.

7.2 Adjustments for Covariates

Multivariate models using cognitive or function assessments as the dependent variables will be adjusted for treatment arm [lanabecestat (20mg, 50 mg) or placebo], baseline cognitive score, years of education (categorical), and age.

7.3 Handling of Dropouts or Missing Data

Dropout subjects will not be replaced in this study. For situations with no rules for handling missing data the default will be no imputation.

Likelihood-based mixed effects models for repeated measures will be used to handle missing data for the cognitive/functional assessment mean CFB analyses. The model parameters are simultaneously estimated using restricted likelihood estimation incorporating all of the observed data. Estimates have been shown to be unbiased when the missing data are missing at random and when there is ignorable non-random missing data.

Repeated measures analyses will only use data from visits where the data was scheduled to be collected. When subjects discontinue from the study early, there may be efficacy data measurements at visits where the variables were not scheduled to be collected. These data will appear in listings only.

Avid Radiopharmaceuticals
Study AV-1451-PX01

Statistical Analysis Plan

7.4 Interim Analyses and Data Monitoring

No interim analysis or data monitoring is planned for this study.

7.5 Multi-center Studies and Pooling of Centers

The data from all centers will be pooled. The pooled data will be analyzed and presented.

7.6 Multiple Comparisons/Multiplicity

No multiple comparisons/multiplicity adjustment is planned.

7.7 Examination of Subgroups

Subgroups of interest will be age, sex, and CDR Global group (see section 8.4.4).

8 STATISTICAL ANALYSIS

8.1 Analysis Population

Five readers independently interpreted the 205 flortaucipir PET scans collected from the AZES PET sub-study. No new subjects were enrolled for the purpose of this study.

Valid images were considered unevaluable in the present study only if 3 out of 5 readers independently declare the image unevaluable for the same reason. Subjects with invalid or unevaluable PET data were excluded from analyses. Criteria for declaring an image invalid or not evaluable is specified in the Image Review Charter. The majority read on each flortaucipir scan (baseline) from these 5 readers was used to determine the tau status of the corresponding study subject.

Subject disposition and baseline characteristics will be summarized using the entire analysis population (regardless if the baseline scan was evaluable or not). Analyses outlined in section 8.4 will be summarized using subjects in the analysis population who have a valid visual tau interpretation as described in section 6.4.1.1.

8.2 Summary of the Analysis Population

The analysis population will be summarized in the disposition table by total available scans, scans read, and breakdown of majority read (detailed in section 6.4.1.1).

8.3 Demographic and Other Baseline Characteristics

Demographics and baseline summaries will be reported on the analysis population. Age (years), sex, education (categorical: 1-5, 6-9, 10-12, 13+ years), race, ethnicity, treatment (lanabecestat – , 2-0 mg or 50 mg –or placebo), florbetapir SUV_r (referenced to the cerebellum), ApoE4 (E4+/E4-), ADAS-Cog11, CDR-SB, CDR Global (categorical: 0, 0.5, 1, 2, 3), FAQ, and MMSE will be reported in a table by enrolling diagnosis in the AZES study (AD or MCI).

8.4 Analysis of Efficacy Parameters

8.4.1 Analysis of Primary Efficacy Variable

8.4.1.1 Risk Ratio of τ AD⁺⁺ vs. Non- τ AD⁺⁺ Subjects in Progression to Clinically Meaningful Deterioration Evaluated by CDR-SB at 18 Months

This analysis will test the hypothesis that the risk of progressing to a clinically meaningful event (≥ 1 change) as determined by CDR-SB value change at 18 months will be significantly greater for subjects in the τ AD⁺⁺ group as compared to those in the non- τ AD⁺⁺ group (τ AD⁻ and τ AD⁺).

Since the study goal is to evaluate the risk ratio of τ AD⁺⁺ group vs non- τ AD⁺⁺ group at month 18 instead of marginal risk ratio by tau status, only month 18 measurements will be included for this analysis.

As described in section 6.4.1.2, the primary efficacy variable will be the dichotomized CDR-SB score CFB (1 point or more increase vs. otherwise). Incidence of this clinically meaningful event by tau visual read groups will be compared using a log-linear model adjusted for treatment arm (lanabecestat – 20 mg or 50 mg, or placebo), baseline age, years of education (categorical), and baseline CDR-SB score. The Poisson distribution will be chosen to describe the distribution of the dependent variable and a log link function will be used to model the risk ratio. To improve the model's stability and reliability, a modified Poisson regression [Zou, 2004] model will be used using a robust error variance estimation, although there is only one observation per subject.

The risk ratio of τ AD⁺⁺ rated subjects progressing to the event over non- τ AD⁺⁺ rated subjects along with the 95% confidence interval will be provided.

8.4.2 Analysis of Secondary Efficacy Variable

8.4.2.1 Risk Ratio of τ AD⁺⁺ vs. Non- τ AD⁺⁺ Subjects in Progression to Clinically Meaningful Deterioration Evaluated by MMSE at 18 Months

The same analysis as described in section 8.4.1.1 will be performed for MMSE, however a CFB in MMSE ≤ -3 will be considered clinically meaningful.

8.4.2.2 Risk Ratio of τAD^{++} vs. Non- τAD^{++} Subjects in Progression to Clinically Meaningful Deterioration Evaluated by ADAS-Cog11 at 18 Months

The same analysis as described in section 8.4.1.1 will be performed for ADAS-Cog11, however a CFB in ADAS ≥ 4 will be considered clinically meaningful.

8.4.2.3 Risk Ratio of τAD^{++} vs. Non- τAD^{++} Subjects in Progression to Clinically Meaningful Deterioration Evaluated by FAQ at 18 Months

The same analysis as described in section 8.4.1.1 will be performed for FAQ, however a CFB in FAQ ≥ 3 will be considered clinically meaningful.

8.4.2.4 Risk Ratio of τAD^{++} vs. Non- τAD^{++} Subjects in Progression to Clinically Meaningful Deterioration Evaluated by CDR Global at 18 Months

The same analysis as described in section 8.4.1.1 will be performed for CDR Global, however a CFB in CDR Global > 0 will be considered clinically meaningful

8.4.2.5 Mixed Model Repeated Measures for Comparison of τAD^{++} vs. Non- τAD^{++} CDR-SB Change at 18 Months

The objective of this analysis is to test the hypothesis that baseline tau status as determined by the flortaucipir scan will predict subjects' cognitive deterioration.

This analysis will test the hypothesis that the CDR-SB CFB at 18 months will be significantly larger (worse) for the τAD^{++} group compared to the non- τAD^{++} group (τAD^{-} and τAD^{+}). The null hypothesis is that the least squares mean (LSM) difference between τAD^{++} and non- τAD^{++} groups at the month 18 visit equals zero.

This hypothesis will be tested using a mixed model repeated measures (MMRM). MMSE CFB will be the dependent variable. The model will include tau status, visit, and the tau status-visit interaction as fixed effects, and be adjusted for treatment arm (lanabecestat – 20 mg or 50 mg, or placebo), baseline CDR-SB score, age, and years of education (categorical) as covariates.

An unstructured covariance matrix will be used to model the within-subject variance-covariance. If the unstructured covariance structure matrix results in a lack of model convergence, the following tests will be used in sequence: heterogeneous Toeplitz covariance structure, heterogeneous autoregressive covariance structure, and compound symmetry covariance structure. The Kenward-Roger approximation will be used to estimate the denominator degrees of freedom.

Descriptive statistics for the CDR-SB at baseline and all scheduled follow-up visits will be summarized by tau read status. The CFB to all follow-ups will be summarized in the same corresponding table.

CDR-SB LSM change will be graphed across time by $\tau AD++$ and non- $\tau AD++$ groups.

8.4.2.6 MMRM for Comparison of $\tau AD++$ vs. Non- $\tau AD++$ MMSE Change at 18 Months

The same analyses will be performed as described in Section 8.4.2.5 with the substitution of MMSE for CDR-SB.

8.4.2.7 MMRM for Comparison of $\tau AD++$ vs. Non- $\tau AD++$ ADAS-Cog11 Change at 18 Months

The same analyses will be performed as described in Section 8.4.2.5 with the substitution of ADAS-Cog11 for CDR-SB.

8.4.2.8 MMRM for Comparison of $\tau AD++$ vs. Non- $\tau AD++$ FAQ Change at 18 Months

The same analyses will be performed as described in Section 8.4.2.5 with the substitution of FAQ for CDR-SB.

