5.4.2. Secondary Objective Analysis

5.4.2.1. Clinically Meaningful Deterioration at 18 Months by Tau Status

To fully assess the prognostic value of tau scan, these CMDs will be assessed for the secondary objective analysis:

- 1) MMSE decreased by 3 points or more;
- 2) ADAS Cog-11 increased by 4 points or more;
- 3) FAQ increased by 3 points or more;
- 4) CDR global with any increase.

The analyses will be identical to what is described in section 5.4.1, with dependent variables 1-4 for CMDs as described above, and the adjustment of corresponding baseline scores.

5.4.2.2. Mean Change of Cognitive/Functional Assessments at 18 Months by flortaucipir PET visual interpretation (τ AD⁺⁺ vs. non- τ AD⁺⁺)

To assess the mean change of CDR-SB, MMSE, ADAS, and FAQ at 18 month by tau status, a mixed model with repeated measures (MMRM) will be used. For each analysis, the change from baseline value from relative measurement will be the dependent variable, and the model will include the fixed effects of tau status (τ AD⁺⁺ or non- τ AD⁺⁺), visit (categorical covariate), tau status-by-visit interaction, and therapeutic treatment assignment from AZES study, as well as corresponding baseline measurement score, and baseline age as continuous covariates. The null hypothesis is that the least squared mean contrast between τ AD⁺⁺ and non- τ AD⁺⁺ groups at month 18 visit equals zero. An unstructured covariance matrix will be used to model the within-

subject variance-covariance. If the unstructured covariance structure matrix results in a lack of convergence, the following tests will be used in sequence: heterogeneous Toeplitz covariance structure, heterogeneous autoregressive covariance structure, and compound symmetry covariance structure. The Kenward-Roger approximation will be used to estimate the denominator degrees of freedom.

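### SAP 8.4.2.5 names MMSE change as the response in the CDR-SB mean-change model, and the substitution rule carries the error into the ADAS-Cog11 and FAQ models

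*SAP*

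**What the plan says.** SAP 8.4.2.5 specifies the MMRM for CDR-SB change at 18 months. Its hypothesis is that "CDR-SB CFB at 18 months will be significantly larger (worse) for the" τAD++ group than for the non-τAD++ group. The model description that follows says "MMSE CFB will be the dependent variable". The adjustment terms then include "baseline CDR-SB score, age, and years of education (categorical) as covariates". The outputs return to CDR-SB: "Descriptive statistics for the CDR-SB at baseline and all scheduled follow-up visits will be summarized by tau read status", and "CDR-SB LSM change will be graphed across time by" tau group.

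The other three secondary MMRMs have no model text of their own. SAP 8.4.2.7 says "The same analyses will be performed as described in Section 8.4.2.5 with the substitution of ADAS-Cog11 for CDR-SB", and SAP 8.4.2.8 says "The same analyses will be performed as described in Section 8.4.2.5 with the substitution of FAQ for CDR-SB". SAP 8.4.2.6 does the same for MMSE.

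Protocol 5.4.2.2 gives one rule for all four scales: "For each analysis, the change from baseline value from relative measurement will be the dependent variable". It pairs that response with the baseline score of the same scale.

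**The concern.** The response is the most basic element of a model specification. Here it contradicts the heading and hypothesis above it, the covariate after it, the planned outputs and the protocol. Taken as written, the CDR-SB model would regress MMSE change on baseline CDR-SB, and the result would say nothing about mean CDR-SB change.

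The sentence also matters beyond its own section, because 8.4.2.6 to 8.4.2.8 are built by substitution into it. SAP 8.4.4 (subgroups) and SAP 8.4.5 (subjects who completed 24 months) then rerun the same models.

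Anyone programming or independently checking these analyses has to decide that one sentence of the SAP is to be ignored. The decision is not hard, but a pre-specified plan should not require it. Only the secondary mean-change objective and its repeats are at stake.

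**Working it through.** No power or sample-size figure bears on this point, so the check is textual.

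**Step 1. Scale references within SAP 8.4.2.5.**

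| Element | Scale named |
|---|---|
| Heading | CDR-SB |
| Hypothesis | CDR-SB |
| Dependent variable | MMSE |
| Baseline covariate | CDR-SB |
| Descriptive table | CDR-SB |
| Graph of LSM change | CDR-SB |

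CDR-SB is named 5 times and MMSE once, 6 in all. The one MMSE reference is the response.

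**Step 2. Apply the substitution rule as written.** Replacing CDR-SB with the named scale changes the five CDR-SB references and leaves the response sentence alone, since that sentence does not contain the term being replaced.

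| SAP section | Scale analysed | Response after substitution | Baseline covariate after substitution | Response agrees with Protocol 5.4.2.2? |
|---|---|---|---|---|
| 8.4.2.5 | CDR-SB | MMSE change | CDR-SB | No |
| 8.4.2.6 | MMSE | MMSE change | MMSE | Yes |
| 8.4.2.7 | ADAS-Cog11 | MMSE change | ADAS-Cog11 | No |
| 8.4.2.8 | FAQ | MMSE change | FAQ | No |

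On the literal reading the response is wrong in 3 of 4 models.

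**Step 3. Does other text settle it?** The secondary objective in SAP section 3 lists mean change in all four scales. SAP 6.4.2.1 assigns continuous ADAS-Cog11 and FAQ scores to the secondary analysis of mean change by tau status. Both support each scale having its own response. For CDR-SB the help from section 6 is weaker: SAP 6.4.1.2 assigns the continuous score to an exploratory analysis, although SAP section 3 makes it secondary. No passage expressly corrects the response sentence.

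**Step 4. Would the models really differ?** Yes, in two ways.

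- *Direction.* Higher CDR-SB is worse and higher MMSE is better (SAP 6.4.1.2 and 6.4.2.1), so the stated direction, larger meaning worse, fits CDR-SB and not MMSE.
- *Visits.* The scheduled post-baseline visits are 4 for CDR-SB and FAQ (months 6, 12, 18, 24), 5 for MMSE (adding month 3) and 6 for ADAS (adding months 3 and 15). If all scheduled visits are modelled, an unstructured covariance for k visits has k(k+1)/2 parameters: 4×5/2 = 10 for CDR-SB and FAQ, 5×6/2 = 15 for MMSE and 6×7/2 = 21 for ADAS.

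**Step 5. Reach.** SAP 8.4.4 and 8.4.5 call the same sections, so the same three models recur there. The exploratory MMRMs in 8.4.3.11, 8.4.3.13 and 8.4.3.14 state which scale's change they evaluate and are not counted.

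**The case against.** The strongest reply is that this is a clerical slip with no real ambiguity. The model is introduced as the test of the hypothesis just stated, which concerns CDR-SB change, and the heading, covariate, table, graph, objective and protocol all agree. That stands: the intent is recoverable, and it limits the weight of the point. It does not make the response sentence correct.

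A second reply is that 3 of 4 overstates the reach. Substituting a scale for CDR-SB is most naturally read as running the same analysis on that scale, not as a word replacement. Sections 8.4.2.7 and 8.4.2.8 also name their outcome in their headings, which is the ground for leaving out the exploratory models. A mechanical replacement would even make the MMSE hypothesis say that a larger change is worse, which is the wrong direction for that scale. This has force. On the natural reading only 8.4.2.5 itself is wrong, 1 model of 4; 3 of 4 is the literal reading. Either way there is one faulty sentence, and the repeats are not separate defects. The direction wording has no numerical effect, since SAP 7.1 makes tests two-sided unless otherwise specified.

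**Conclusion.** The concern holds. SAP 8.4.2.5 names the wrong response for the CDR-SB MMRM, against its own section and Protocol 5.4.2.2, and nothing in the SAP corrects it. The size is one erroneous sentence, affecting 3 of 4 secondary mean-change models if the substitution rule is applied literally and 1 of 4 if it is read by intent, with the same models recurring in 8.4.4 and 8.4.5.

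This is an inconsistency in the specification and not a questionable choice of method. The primary risk-ratio analysis (SAP 8.4.1.1), the sample size and the stated power do not depend on it, and no result changes if the analyst uses each scale's own change. It should be corrected because this sentence governs programming and checking. The conclusion assumes only that the protocol's rule, each scale's own change with its own baseline, is what was intended, and the rest of the SAP supports that.

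**What to change.** In SAP 8.4.2.5, change the response sentence to: *CDR-SB CFB will be the dependent variable.* The substitution in 8.4.2.6 to 8.4.2.8 then gives each scale its own change and its own baseline score, as Protocol 5.4.2.2 requires, and the repeats in 8.4.4 and 8.4.5 follow. If programming has already begun, the same line can be issued as a documented correction.

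A separate, optional edit can go in at the same time. SAP 6.4.1.2 dichotomises CDR Global by any change, whereas SAP 6.4.2.2, SAP 8.4.2.4 and Protocol 5.4.2.1 count only an increase. Wording 6.4.1.2 as an increase (change above 0) would bring it into line. The main point does not depend on this.

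The cost is one line, plus one optional wording change, with no new data or analyses.

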2 INTRODUCTION

Brain amyloid plaques, composed of amyloid-beta ($A\beta$) aggregates, and neurofibrillary tangles, composed of phosphorylated aggregated tau deposits, are defining pathological features of Alzheimer's disease (AD). Thus, an amyloid negative florbetapir positron emission tomography (PET) scan of the brain, which indicates the absence of moderate or frequent $A\beta$ neuritic plaques, is inconsistent with a diagnosis of AD. However, because amyloid is believed to accumulate very early in the AD process (Jack et al. 2010) and may be present in clinically normal elderly subjects (Price and Morris 1999; Sperling et al. 2011), the density or distribution of amyloid in subjects with a positive scan is not thought to reflect the severity of AD.

In contrast to $A\beta$ neuritic plaques, the density and distribution in the brain of phosphorylated tau, aggregated in neurofibrillary tangles, increases with AD-related cognitive impairment and correlates with neurodegeneration (Duyckaerts et al. 1987). Thus, a PET imaging agent that binds to phosphorylated tau has the potential to indicate disease severity and with longitudinal measures could provide important information on disease progression. The PET tracer (18F-AV-1451) possesses a high affinity to human phosphorylated tau deposits. Up to three scans will be performed over the two year study.

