8.4.3.11 MMRM for Additional Comparisons of CDR-SB Change across Tau Groups

Differences between τ AD++ vs non- τ AD++ LSM changes in CDR-SB at 24 months will also be tested and presented with the secondary analysis outlined in section 8.4.2.5.

Separate models similar to that outlined in 8.4.2.5 will be used to evaluate CDR-SB changes over time between τ AD (τ AD+ and τ AD++) vs τ AD-, and τ AD++ vs τ AD-.

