8.4.5 Sensitivity Analysis

To avoid misinterpretation of potentially biased estimates caused by missing data, the MMRM analyses described in sections 8.4.2.5 through 8.4.2.8 will be run on the set of 90 subjects who completed the 24 month visit.

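### The mean-change MMRMs hold the baseline-score effect equal at every visit, so the month-18 contrast between non-randomised tau groups may be mis-adjusted for baseline severity

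*SAP*

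**What the plan says.** SAP 8.4.2.5 specifies the CDR-SB mean-change model: "The model will include tau status, visit, and the tau status-visit interaction as fixed effects". After treatment arm, the adjustment terms are "baseline CDR-SB score, age, and years of education (categorical) as covariates". Tau-by-visit is the only interaction. Protocol 5.4.2.2 has the same structure: tau-by-visit and treatment assignment, "as well as corresponding baseline measurement score, and baseline age as continuous covariates". The null hypothesis in both documents concerns the τAD++ versus non-τAD++ difference at month 18.

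The specification is inherited throughout:
- SAP 8.4.2.6–8.4.2.8 substitute MMSE, ADAS-Cog11 and FAQ.
- SAP 8.4.3.11 says "Separate models similar to that outlined in 8.4.2.5 will be used to evaluate CDR-SB changes over time", and 8.4.3.12–8.4.3.14 follow suit.
- The sensitivity analysis in SAP 8.4.5 reruns the 18-month MMRMs: they "will be run on the set of 90 subjects who completed the 24 month visit". The population changes; the model does not.

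The primary analysis differs. In SAP 8.4.1.1, "only month 18 measurements will be included for this analysis".

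**The concern.** In a randomised comparison, baseline score is balanced in expectation and a common coefficient mainly affects precision. Here the groups are majority scan reads (SAP 6.4.1.1). SAP section 2 says that tau, "aggregated in neurofibrillary tangles, increases with AD-related cognitive impairment and correlates with neurodegeneration", so the documents themselves give a reason to expect τAD++ subjects to start more impaired. Baseline adjustment is then control of confounding.

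The effect of baseline score on change need not be the same at 6, 12, 18 and 24 months. If worse baseline marks faster decline, its effect on change grows with follow-up. If it reflects regression to the mean, it may be flat or shrink. A single coefficient averages over visits and leans towards the early, less variable ones. What it misses at month 18 can go only into the tau-by-visit term, which is the term being tested. Part of a baseline-severity difference could then be reported as a tau-status difference.

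**Working it through.** **The plan's own figure.** The only stated operating characteristic is 90% power for the primary risk ratio (205 subjects, 75/25 split, 40% reference risk, risk ratio 1.65, hence 66%; SAP 4.5). It reproduces. With pooled risk 0.595, the null SE is √[0.595 × 0.405 × (1/51.25 + 1/153.75)] = 0.0792 and the alternative SE is √[0.24/51.25 + 0.2244/153.75] = 0.0784. Power is Φ[(0.26 − 1.96 × 0.0792)/0.0784] = 90.9%. It does not bear on the MMRMs, for which no power is stated.

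**Inputs from the documents.** 205 subjects; 75% τAD++ (from Study TZAX); CDR at months 6, 12, 18 and 24; month 24 available in about 90.

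**Assumed inputs (CDR-SB only).**
- Within-group baseline SD 1.0; baseline gap Δ between tau groups 0.5 or 1.0 point.
- Random-slope SD σs of 1.2–2.0 points per 18 months; visit error SD σe of 0.8–1.0.
- Time t = 1/3, 2/3, 1, 4/3 (1 = month 18); covariance V = σs²tt′ + σe²I, taken as known.
- Baseline effect at month 18 of 0.3 points per baseline point, except where varied.

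Age, education and treatment arm are left out of the calculation.

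**Step 1: bias formula.** Because tau is free at each visit, the expected month-18 contrast is off by (β18 − β̄) × Δ. Here β18 is the true baseline effect at month 18, and β̄ = 1′Mβ/1′M1 is the pooled coefficient, with M the sum of subjects' inverse covariance matrices.

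**Step 2: share of the month-18 effect captured.** For an effect proportional to time and visits to month 18 only, β̄/β18 reduces to 6σe²/(9σe² + 2σs²):
- σs = 1.2, σe = 1.0: 6/(9 + 2.88) = 0.505
- σs = 2.0, σe = 0.8: 3.84/(5.76 + 8) = 0.279

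Adding month 24 in 90 subjects moves the range to 23–49%; with month 24 in everyone it would be 19–46%.

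**Step 3: bias at month 18.** The smallest value is 0.3 × (1 − 0.505) × 0.5 = 0.074. The largest, at 23.4% capture with month 24 included, is 0.3 × 0.766 × 0.5 = 0.1149. At Δ = 1.0 these double to 0.15 and 0.23.

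**Step 4: SE and rejection.** With baseline-by-visit, SE = √{(σs² + σe²)/205 × [1/(0.75 × 0.25) + Δ²/1.0²]}. At Δ = 0.5 this runs from √(2.08/205 × 5.583) = 0.24 to √(5/205 × 5.583) = 0.37; at Δ = 1.0, from 0.25 to 0.39. The planned model's SE is 0.23–0.36 and 0.24–0.37. Under proportional growth, bias/SE is 0.27–0.38 and 0.53–0.74. Rejection under no tau effect is P(|Z + bias/SE| > 1.96).

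| Baseline effect at 6/12/18/24 months | Bias, Δ = 0.5 | Bias, Δ = 1.0 | Rejection, Δ = 0.5 | Rejection, Δ = 1.0 |
|---|---|---|---|---|
| 0.10/0.20/0.30/0.40 (proportional) | 0.07 to 0.11 | 0.15 to 0.23 | 6–7% | 8–11% |
| 0.05/0.10/0.15/0.20 (proportional, half size) | 0.04 to 0.06 | 0.07 to 0.11 | about 5% | 6–7% |
| 0.20/0.25/0.30/0.33 (milder growth) | 0.04 to 0.06 | 0.07 to 0.11 | about 5% | 6–7% |
| constant | 0 | 0 | 5% | 5% |
| 0.40/0.35/0.30/0.25 (shrinking) | −0.04 to −0.06 | −0.07 to −0.12 | about 5% | 6–7% |

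With baseline-by-visit the bias is 0 in every row, for 1.5–1.9% more SE at Δ = 0.5 and 5.7–7.1% at Δ = 1.0.

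**Step 5: second check by simulation.** This used an estimated unstructured covariance and different assumptions: 154 versus 51 subjects, month 24 in a random 90, baseline SD 1.3, residual SDs 1.2/1.7/2.2/2.7, and correlation 0.7 per visit step. With proportional effects of 0.15–0.45 at month 18 and gaps of 0.4–1.3 points, the planned model overstated the contrast by 0.03–0.35 points more than the baseline-by-visit model. The excess was about zero with no gap or a constant effect. Under no tau effect, rejection was 6.3% (effect 0.30, gap 0.65), 11.6% (0.30, 1.3) and 18.3% (0.45, 1.3), against 4.5–4.7% with the interaction.

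**The case against.** A common baseline coefficient is a legitimate prespecified model, and protocol and SAP agree on it. The bias needs two things the documents do not show: a baseline gap between the tau groups, and a baseline effect that changes over visits. SAP section 2 supports only the first, and in general terms; the cohort is range-restricted (amyloid positive, MMSE 20–30, CDR global 0.5 or 1). With an assumed SD of 1.0, a 1.0-point gap is a full SD. That the interaction removes all bias follows from how the scenarios were generated.

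Nor is the fix clearly better on mean squared error. The ratio of the planned model to the fix is 0.985–1.002 (Δ = 0.5) and 0.946–1.007 (Δ = 1.0) under milder growth, and similar under shrinkage. It exceeds 1 materially only under proportional growth at 0.3 (1.05–1.11 and 1.16–1.38). If the effect is constant, the planned model wins outright: 1/1.019² to 1/1.015², about 0.96–0.97, and 1/1.071² to 1/1.057², about 0.87–0.90.

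There are also safeguards. The risk ratios cover every MMRM scale at month 18 with baseline adjustment. SAP 8.4.2.5 adds that "Descriptive statistics for the CDR-SB at baseline and all scheduled follow-up visits will be summarized by tau read status". The analyses are repeated by baseline CDR Global (SAP 8.4.4).

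All of this stands, and it limits the size and priority of the point. It does not remove it: tabulation would reveal an imbalance and subgrouping would narrow it, but neither supplies the missing term. Age, education and treatment arm are also main effects only. Baseline score is singled out because it is the covariate that the SAP's own rationale links to tau status.

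**Conclusion.** The concern holds as a conditional risk to secondary and exploratory analyses, not as a demonstrated error. The planned MMRMs are unbiased on this point only if the tau groups have equal mean baseline scores or the baseline effect at month 18 equals the pooled one, as it does when constant. Otherwise the sign follows the time course: overstated if the effect grows and τAD++ subjects start worse, understated if it shrinks.

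For CDR-SB, the strongest growth pattern in the main calculation gives at most 0.23 points (0.74 SE); milder patterns give 0.04–0.12 in either direction. Every magnitude rests on the assumed gap, variances and time course above. Nothing was computed for MMSE, ADAS-Cog11 or FAQ. The primary modified Poisson analysis and the secondary risk ratios use month 18 only and are not affected. This is worth considering because the correction is cheap, with medium confidence that it matters in practice.

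**What to change.** Add baseline score-by-visit as a fixed effect in SAP 8.4.2.5, state that 8.4.2.6–8.4.2.8, 8.4.3.11–8.4.3.14 and 8.4.5 inherit it, and make the same change in protocol 5.4.2.2. Alternatively, keep the planned model and add a month-18-only ANCOVA with the same covariates as a sensitivity analysis. For CDR-SB that loses no subjects, since all 205 were selected for having a month-18 CDR. It also leaves the planned model in place if comparability with Study A05C matters; that study's model is not given in these documents.

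The interaction costs one line per document and no new data. It uses three degrees of freedom for CDR-SB and FAQ with month 24 in the model (two without), four for MMSE and five for ADAS-Cog11, plus the SE increase shown above. The SAP describes the reads as done and the outcome database is locked, so the change should be dated before scores by tau group are examined, or labelled post hoc. The same paragraph of SAP 8.4.2.5 names MMSE change as the dependent variable of the CDR-SB model; correct that in the same edit.
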